The secondary outcomes will be summarized in [Table 22](#) through [Table 34](#). [Table 22](#) and [Table 24](#) will present clearance rates for the amebiasis group with 95% confidence intervals on Days 3, 5, and 7 for the treatment and placebo groups, as well as the differences in clearance rates and 95% confidence intervals for the differences. [Table 23](#) and [Table 25](#) are analogous tables for the giardiasis group. [Table 26](#) will present the coefficient estimates for the mixed effects model for the amebiasis group. [Table 27](#) is the analogous table for the giardiasis group. [Table 28](#) will present the proportion of subjects in the amebiasis group with negative stool antigen test on Days 1, 3, 5, 7, and 14. This outcome is not analyzed for the giardiasis group. [Table 29](#) will present the proportion of subjects with sustained cure for the amebiasis group on days 7, 14, and 28, for each treatment arm, with 95% confidence intervals, as well as the difference in proportions between treatment arms and 95% confidence interval for the difference. [Table 30](#) will present analogous summaries for the giardiasis group (Day 5 instead of Day 7). [Table 31](#) will present the proportion of subjects in the amebiasis group with relapse by Day 14, the proportion with reinfection by Day 14, and the proportion with either relapse or reinfection by Day 14, separately for each treatment arm, with 95% confidence intervals. [Table 32](#) is the analogous table for the giardiasis group. Differences in proportions between treatment arms and 95% confidence intervals for the differences will also be included. [Table 33](#) will present a perfectly analogous summary for Day 28 rather than Day 14, for the amebiasis group. [Table 34](#) is the analogous table for the giardiasis group. [Listing 15](#) and [Listing 16](#) provide a listing for all efficacy endpoints for the amebiasis groups; [Listing 17](#) and [Listing 18](#) are the analogous listings for the giardiasis groups.

The secondary outcomes for the symptomatic population are identical to those for the asymptomatic population with the following exceptions:

- Parasitological response is defined differently, and parasitological response on Day 5 (giardiasis) and Day 7 (amebiasis) were changed from primary to secondary.
- Time to resolution of diarrhea was added as an endpoint.

The outcomes that are identical to the asymptomatic population will be analyzed identically. Parasitological response on Day 5 (giardiasis) and Day 7 (amebiasis) will be analyzed by the methods planned for parasitological response on the other study days, described above. Kaplan-Meier curves and log rank tests will be used to compare time to diarrhea resolution between the treatment and control arm for each disease group ([Figure 4](#)).

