3.1.2. Objectives for the Symptomatic Population

Primary *E. histolytica*:

To compare the proportion of subjects with stools positive by rapid EIA and positive antigen detection EIA for *E. histolytica* at enrollment with resolution of diarrhea (less than 3 loose stools/ 24 hours) by Day 7.

Secondary *E. histolytica*:

- To compare the proportion of subjects with positive rapid EIA and positive antigen detection EIA for *E. histolytica* and trophozoites on smear (wet mount or concentrated trichrome) at enrollment with parasitological response (no detection of trophozoites on microscopic exam) by Day 7.
- To compare the proportion of subjects with positive rapid EIA and positive antigen detection EIA for *E. histolytica* and trophozoites on smear at enrollment with parasitological response (no detection of trophozoites on microscopic exam) by Day 3 and 5.
- To compare the rate of decrease in trophozoite/cyst load by qPCR in stools by Days 3, 5, and 7.
- To compare the proportion of subjects with negative stool antigen test by Days 3, 5, 7, and 14.
- To compare the proportion of subjects with sustained cure (no detection of trophozoites by microscopic exam) at 14 and 28 days.
- To compare the proportion of subjects with relapse (same strain) or re-infection (new strain) with positive stools at 14 and/or 28 days by genotyping the initial vs. subsequent strain.
- To compare the time to resolution of diarrhea (less than 3 loose stools/24 hours)

Primary *Giardia*:

To compare the proportion of subjects with stool positive rapid EIA and positive antigen detection EIA for *Giardia* at enrollment with resolution of diarrhea (less than 3 loose stools/24 hours) by Day 5.

Secondary *Giardia*:

- To compare the proportion of subjects with parasitological response (no detection of trophozoites on microscopic exam) by Day 3 and 5.
- To compare the rate of decrease in trophozoite/cyst load by qPCR in stools by Days 3 and 5.
- To compare the proportion of subjects with negative stool antigens by days 3 and 5.
- To compare the proportion of subjects with sustained cure (no detection of trophozoites by microscopic exam) at 14 and 28 days.
- To compare the proportion of subjects with relapse (same strain) or re-infection (new strain) with positive stools at 14 and/or 28 days by genotyping the initial vs. subsequent strain.
- To compare the time to resolution of diarrhea (less than 3 loose stools/24 hours)

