3.2.2. Symptomatic Population Endpoints

Primary Outcome Measures

1. Proportion of subjects with positive rapid EIA and positive antigen detection EIA for *E. histolytica* and resolution of diarrhea (less than 3 loose stools/ 24 hours) by Day 7.
2. Proportion of subjects with positive rapid EIA and positive antigen detection EIA for *Giardia* and resolution of diarrhea (less than 3 loose stools/24 hours) by Day 5.

Secondary Outcome Measures

1. *E. histolytica*:

- a. Proportion of subjects with positive rapid EIA and positive antigen detection EIA for *E. histolytica* and trophozoites on smear at enrollment with parasitological response (no detection of trophozoites on microscopic exam) by Day 7.
- b. Proportion of subjects with positive rapid EIA and positive antigen detection EIA for *E. histolytica* and trophozoites on smear at enrollment with parasitological response (no detection of trophozoites on microscopic exam) by Day 3 and 5.
- c. Rate of decrease of trophozoite/cyst load by qPCR in stools by Days 3, 5, and 7
- d. Proportion of subjects with negative stool antigen test by Days 3, 5, 7, and 14
- e. Proportion of subjects with sustained cure (no detection of trophozoites by microscopic exam) at 14 and 28 days
- f. Proportion of subjects with relapse (same strain) or re-infection (new strain) with positive stools at 14 and 28 days by genotyping the initial vs. subsequent strain
- g. Time to resolution of diarrhea (less than 3 loose stools/24 hours)

2. *Giardia*:

- a. Proportion of subjects with positive rapid EIA and positive antigen detection EIA for *Giardia* and trophozoites on smear at enrollment with parasitological response (no detection of trophozoites on microscopic exam) by Day 3 and 5
- b. Rate of decrease of trophozoite/cyst load by qPCR in stools by Days 3 and 5
- c. Proportion of subjects with negative stool antigens by days 3 and 5.
- d. Proportion of subjects with sustained cure (no detection of trophozoites by microscopic exam) at 14 and 28 days
- e. Proportion of subjects with relapse (same strain) or re-infection (new strain) with positive stools at 14 and 28 days by genotyping the initial vs. subsequent strain
- f. Time to resolution of diarrhea (less than 3 loose stools/24 hours)

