4.5. Efficacy and Safety Variables

4.5.1. Efficacy Variables

[Table 4](#) and [Table 5](#) summarize the efficacy variables and time points for the asymptomatic and symptomatic populations, respectively.

Table 4: Efficacy Variables for the Asymptomatic Study Population

Outcome Type	Outcome	Time points, Asymptomatic amebiasis group	Time points, Asymptomatic giardiasis group
Primary	Parasitological response (no detection of cysts or trophozoites on microscopic exam or negative antigen detection)	Day 7	Day 5
Secondary	Parasitological response (no detection of cysts or trophozoites on microscopic exam or negative antigen detection)	Days 3 and 5	Day 3
	Rate of decrease in trophozoite/cyst load by qPCR in stools	Days 3, 5, and 7	Days 3 and 5
	Negative stool antigen test	Days 3, 5, 7, and 14	N/A
	Sustained cure (no detection of cysts or trophozoites by microscopic exam or negative antigen detection)	Days 14 and 28	Days 14 and 28
	Relapse (same strain) or re-infection (new strain) with positive stools by genotyping the initial vs. subsequent strain.	Day 14 and/or 28	Day 14 and/or 28

Table 5: Efficacy Variables and Time Points for the Symptomatic Study Population

Changes from outcomes for the asymptomatic population are shown in blue:

Outcome Type	Outcome	Time points, Symptomatic amebiasis group	Time points, Symptomatic giardiasis group
Primary	Resolution of diarrhea ^a	Day 7	Day 5
Secondary	Parasitological response (no detection of trophozoites on microscopic exam ^b)	Days 3, 5, and 7 ^c	Day 3 and 5 ^c
	Rate of decrease in trophozoite/cyst load by qPCR in stools	Days 3, 5, and 7	Days 3 and 5
	Negative stool antigen test	Days 3, 5, 7, and 14	Days 3 and 5
	Sustained cure (no detection of trophozoites by microscopic exam) ^d	Days 14 and 28	Days 14 and 28
	Relapse (same strain) or re-infection (new strain) with positive stools by genotyping the initial vs. subsequent strain.	Day 14 and/or 28	Day 14 and/or 28
	Time to resolution of diarrhea	Assessment over the study period	Assessment over the study period

^a New outcome for the symptomatic population^b The definition of parasitological response was revised to allow for cysts and remove the antigen test.^c Moved from primary to secondary outcome.^d The definition of “cure” was updated to match the updated definition of “parasitological response”.

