Table 28: Comparison of Proportion of Subjects with Negative Stool Antigen Test between Auranofin Group and Placebo Group, Asymptomatic Amebiasis Group

		Proportion with negative stool antigen tests (95% CI) on the specified day					
	Number of Subjects	During Screening	Day 1	Day 3	Day 5	Day 7	Day 14
Auranofin, 6 mg							
Placebo							
Difference in clearance rates (95% CI)							

Note: These analyses will be performed both on the m-ITT population and the per-protocol population.
 Footnote 1: The method for CI calculation will be denoted here.

Table will be repeated for the symptomatic population

Table 29: Comparison of Proportion of Subjects with Sustained Cure between Auranofin Group and Placebo Group, Asymptomatic Amebiasis Group

		Proportion with sustained cure on the specified day and 95% CI		
	Number of Subjects	Day 7	Day 14	Day 28
Auranofin, 6 mg				
Placebo				
Difference in clearance rates (95% CI)				

The following definitions are for the asymptomatic amebiasis group:
Sustained cure on Day 14 is defined as no detection of cysts or trophozoites on microscopic exam or negative antigen detection on Days 7 and 14.
Sustained cure on Day 28 is defined to be no detection of cysts or trophozoites on microscopic exam or negative antigen detection on Days 7, 14, and 28.
Note: These analyses will be performed both on the m-ITT population and the per-protocol population.
Footnote 1: The method for CI calculation will be denoted here.

Table will be repeated for the symptomatic population.

Footnotes for the repeat table:

Sustained cure on Day 14 is defined to be no detection of trophozoites on microscopic exam on Days 7 and 14.

Sustained cure on Day 28 is defined to be no detection of trophozoites on microscopic exam on Days 7, 14, and 28.

Table 30: Comparison of Proportion of Subjects with Sustained Cure between Auranofin Group and Placebo Group, Asymptomatic Giardiasis Group

		Proportion with sustained cure on the specified day and 95% CI		
	Number of Subjects	Day 5	Day 14	Day 28
Auranofin, 6 mg				
Placebo				
Difference in clearance rates (95% CI) for the difference				

The following definitions are for the asymptomatic giardiasis group:
Sustained cure on Day 14 is defined to be no detection of cysts or trophozoites on microscopic exam or negative antigen detection on Days 5 and 14.
Sustained cure on Day 28 is defined to be no detection of cysts or trophozoites on microscopic exam or negative antigen detection on Days 5, 14, and 28.

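### The SAP lists negative stool antigen on Days 3 and 5 as a secondary outcome for symptomatic giardiasis, but its analysis section says without qualification that the outcome is not analysed in giardiasis and gives it no table.

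*SAP*

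**What the plan says.** For symptomatic giardiasis the SAP sets the objective "To compare the proportion of subjects with negative stool antigens by days 3 and 5" (3.1.2) and the endpoint "Proportion of subjects with negative stool antigens by days 3 and 5" (3.2.2). Tables 3 and 5 carry a row for "Negative stool antigen test" with Days 3 and 5 in the symptomatic giardiasis column. Protocol 3.2.2 lists the same outcome on the same days. For asymptomatic giardiasis, SAP Tables 2 and 4 mark it as not applicable.

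SAP 8.2.1 assigns outputs, opening with "The secondary outcomes will be summarized in" Tables 22 to 34. After describing Table 28, the antigen table for amebiasis, it adds: "This outcome is not analyzed for the giardiasis group". The next paragraph turns to symptomatic subjects: "The secondary outcomes for the symptomatic population are identical to those for the asymptomatic population with the following exceptions". Two exceptions follow: the changed definition and status of parasitological response, and the new time-to-resolution endpoint.

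SAP 8.2.2 lists four asymptomatic giardiasis outcomes, none of them antigen on its own. It closes by saying that symptomatic giardiasis secondaries are handled in the same way as those for symptomatic amebiasis.

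**The concern.** The sections that define the outcomes and the section that assigns their analyses give different instructions. Under 3.1.2, 3.2.2 and Tables 3 and 5, a programmer would compare the arms on antigen in symptomatic giardiasis. Under 8.2.1 and the table shells, no such comparison would be produced.

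For symptomatic subjects the SAP took antigen out of the definition of parasitological response (Table 3, first footnote; 3.3). The stand-alone antigen outcome is therefore the only planned antigen comparison in symptomatic giardiasis, and nothing else in the plan would replace it.

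The outcome also has some particular value in this trial. The primary outcome is self-reported diarrhea (SAP 4.5.1), active and placebo capsules can be told apart, and laboratory staff are the only group treated as fully blind (SAP 4.4.2). If the plan leaves it open whether to report or omit a laboratory-assessed secondary, the choice could be made after the results are known.

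**Working it through.** No power, alpha or event figure bears on this point, so the check sets the relevant places side by side.

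**1. Is the outcome pre-specified?** Yes. It appears in Protocol 3.1 and 3.2.2, and in the SAP four times: Table 3, 3.1.2, 3.2.2 and Table 5.

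**2. Can the 8.2.1 sentence be read as covering asymptomatic subjects only?** Not from its wording. The same paragraph cites Tables 24 and 25 and Listings 16 and 18, all of which are symptomatic outputs. It covers both populations, and the sentence carries no limit.

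**3. Does the next paragraph restore the outcome?** No. It makes the symptomatic outcomes the same as the asymptomatic ones apart from two exceptions. Asymptomatic giardiasis has no stand-alone antigen outcome (Tables 2 and 4; 8.2.2), and its addition for symptomatic giardiasis is not one of the exceptions. Read literally, this paragraph also leaves it out.

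**4. Is there a table?** The secondary range holds 34 − 22 + 1 = 13 tables:

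| Outcome | Amebiasis | Giardiasis |
|---|---|---|
| Clearance | 22, 24 | 23, 25 |
| Mixed model for parasite load | 26 | 27 |
| Negative antigen | 28 | none |
| Sustained cure | 29 | 30 |
| Relapse or reinfection | 31, 33 | 32, 34 |

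That is 7 amebiasis and 6 giardiasis tables, 7 + 6 = 13. The difference of one is antigen. The title of Table 28 is "Comparison of Proportion of Subjects with Negative Stool Antigen Test between Auranofin Group and Placebo Group, Asymptomatic Amebiasis Group", and the note beneath it reads "Table will be repeated for the symptomatic population". The note therefore gives symptomatic amebiasis. Wherever the SAP wants a giardiasis version, it provides a separately numbered table.

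**5. Does any other output fill the gap?** Listing 18 shows antigen results by subject, study day and treatment group for symptomatic giardiasis. It is a data listing and makes no comparison between arms.

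**6. What is at stake in number?** One outcome × two days = 2 comparisons, planned in 34 + 34 = 68 subjects, each to be run in the mITT and per-protocol populations (SAP 6.3).

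**7. Are the days consistent?** Not in the protocol's statistical section. Protocol 11.1 gives giardiasis antigen on Days 3, 5 and 7, and 11.4 breaks off after Day 3. Every other place gives Days 3 and 5. Protocol 7.3.6 takes Day 7 stool from amebiasis subjects only, although Protocol 8.2.1 lists Day 7 collection without that limit.

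**The case against.** The strongest reply is that the SAP already contains an instruction to analyse the outcome. SAP 8.2.2 carries symptomatic giardiasis over from symptomatic amebiasis, where antigen is a secondary. SAP 6.3 applies both analysis populations to all secondary endpoints, and 6.5 gives one method for all the binary ones. The 8.2.1 sentence is correct for asymptomatic giardiasis and directly follows the description of a table titled for asymptomatic amebiasis. SAP section 15 records that version 2.0 added the symptomatic endpoints, so the sentence is probably leftover wording.

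Most of this stands. It shows a likely intention to analyse and supplies a method. It does not remove the conflict, because 8.2.2 names no outcome, day or table, while 8.2.1 excludes this outcome expressly.

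A reader might infer three stronger things that the documents do not support:

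- **That the outcome has been dropped.** Four places in the SAP keep it, 8.2.2 points towards analysis, and Listing 18 reports the individual results.
- **That the SAP's exclusion overrides the protocol.** The precedence clause in Protocol 11.4 concerns the language of that section. It does not reach the outcome list in Protocol 3.2.2, and it cannot settle a conflict inside the SAP.
- **That giardiasis loses its laboratory-blinded evidence.** Microscopy (Table 25), parasite load (Table 27), sustained cure (Table 30) and relapse or reinfection (Tables 32 and 34) all keep giardiasis tables, either as symptomatic tables or with a note to repeat them for that population.

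**Conclusion.** The contradiction is real, and it lies inside the SAP. If 8.2.1 and the shells are followed, the Day 3 and Day 5 antigen comparisons in symptomatic giardiasis (planned 34 per arm) would not be made, and no other planned comparison uses antigen in that group. If 8.2.2 is followed, they would be made, but without a specified table. The plan does not say which governs.

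The consequence is limited to one secondary outcome in one disease group. The primary analysis, the sample size, data collection and the other giardiasis secondaries are unaffected. The conclusion rests on reading the 8.2.1 sentence as written. That it is a carry-over is likely but cannot be confirmed from the documents. It should be corrected before database lock.

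**What to change.** In the SAP:

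1. In 8.2.1, limit the sentence after Table 28 to the asymptomatic giardiasis group.
2. In the list of symptomatic exceptions in 8.2.1, add negative stool antigen on Days 3 and 5 for giardiasis.
3. Add a symptomatic giardiasis version of Table 28 with Days 3 and 5, for the mITT and per-protocol populations, and cite it in 8.2.1 and 8.2.2.

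In the protocol, reconcile the giardiasis antigen days in 11.1 and 11.4 with the Days 3 and 5 given in 3.1 and 3.2.2. Without this, the new table would still conflict with 11.1.

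The cost is a few lines of text and one table shell. Protocol Appendix B already schedules antigen testing on Days 3 and 5, except for subjects given metronidazole before completing dosing. SAP 6.5 already imputes subjects who stop treatment and receive metronidazole for worsening symptoms as failures on Day 3, 5 and 7 secondaries other than quantitative load. No visit, sample or assay is added.

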8.2.2. Giardiasis Group

The secondary outcomes for the asymptomatic giardiasis group are:

6. Parasitological response (no detection of cysts or trophozoites on microscopic exam or negative antigen detection) by Day 3
7. Rate of decrease of trophozoite/cyst load by qPCR in stools by Days 3,5
8. Proportion of subjects with sustained cure (no detection of cysts or trophozoites by microscopic exam or negative antigen detection) at 14 and 28 days
9. Proportion of subjects with relapse (same strain) or re-infection (new strain) with positive stools at 14 and 28 days by genotyping the initial vs. subsequent strain

These outcomes are analogous to the asymptomatic amebiasis outcomes and will be analyzed using perfectly analogous methods.

Similarly, the secondary outcomes for the symptomatic giardiasis population will be analyzed analogously to those for the symptomatic amebiasis population

9. SAFETY EVALUATION

9.1. Demographic and Other Baseline Characteristics

Summaries of age, sex, ethnicity, and race will be presented by treatment group and overall ([Table 15](#) and [Table 16](#)), for each disease group and study population. Ethnicity is categorized as “Hispanic or Latino”, or “Not Hispanic or Latino”. In accordance with NIH reporting policy, subjects may self-designate as belonging to more than one race or may refuse to identify a race, the latter reflected in the CRF as “No” to each racial option.

Individual subject listings will be presented for all demographics ([Listing 9](#) and [Listing 10](#)); pre-existing medical conditions ([Listing 11](#) and [Listing 12](#)); vital signs and oral temperature ([Listing 31](#) and [Listing 32](#)); and concomitant medications ([Listing 35](#) and [Listing 36](#)). These listings will be presented separately for each disease group and study population.

9.1.1. Prior and Concurrent Medical Conditions

All current illnesses and past pre-existing medical conditions will be MedDRA coded using MedDRA dictionary version 18.1 or higher. Summaries of subjects’ pre-existing medical conditions will be presented by treatment group ([Table 17](#)), disease group, and study population. Individual subject listings will be presented for all medical conditions ([Table 11](#) and [Table 12](#)). Listings are presented separately for each disease group and study population.

9.1.2. Prior and Concomitant Medications

Summaries of medications that were started prior to dosing and continuing at the time of dosing will be presented by WHO Drug classification and treatment group, separately for each disease group and study population ([Table 79](#) and [Table 80](#)). Individual subject listings will be presented for all concomitant medications ([Listing 35](#) and [Listing 36](#)).

9.2. Measurements of Treatment Compliance

In the amebiasis group, all subjects were to receive a total of 7 doses of study product (once a day for 7 days). In the giardiasis group, all subjects were to receive a total of 5 doses of study product (once a day for 5 days). The number of doses of study product administered to subjects will be presented by treatment group as part of the subject disposition tables, separately for each disease group and study population ([Table 9](#) and [Table 10](#)). [Listing 13](#) and [Listing 14](#) list the doses missed and treatment assignment for each subject.

[Table 13](#) summarizes dosing dates by treatment arm, disease group, and study population.

